#### 6.2.2 Blind ing procedu res

There will be no blinding as it is impossible to hide the programming method because the differences are very distinct.

#### 6.2.3 Other methods of minimising bias

Two of the questionnaires used in the study are validated. Two are custom questionnaires but based on similar questionnaires used in a study that was assessing the same narrative aspect as this study aims to measure.

### 6.3 Unblinding P rocedures (Code break)

Not applicable.

### 7. STUDY POPULATION

The study will take place at two sites in canton Bern, Switzerland (Thun and Bern).

### 7.1 Eligibil ity criteria

Participants fulfilling all of the following inclusion criteria are eligible for the study:

- All classifications of hearing loss (sensorineural, conductive, combined)
- If the hearing loss is conductive or combined it must be approved for amplification by a physician
- All shapes of hearing loss (flat, sloping, reverse slope, notch)
- Hearing loss severity ranging from mild to severe
- First time hearing aid users
- German speaking
- Both genders
- Ages 18 and older
- Ability and willingness to sign the consent form

The presence of any one of the following exclusion criteria will lead to exclusion of the participant:

- Contraindications for amplification
- Experienced or current hearing aid users
- Active ear disease
- Inability to follow the procedures of the study due to language problems, psychological disorders, dementia, or other cognitive problems of the participant,
- A reduced mobility making them unable to attend weekly study appointments
- A reduced ability to describe auditory impressions and the usage of the hearing aids
- Uncooperative so that it is not possible to record a valid pure tone audiogram
- A strongly reduced dexterity
- Central hearing disorders
- Bernafon employees
- Family members of Bernafon employees

### 7.2 Recruitment and screening

The participants will be recruited by the Audika call center. The call center has a database of prospective clients that have either come in for a hearing test and not purchased hearing aids or have never come for an appointment. The call center will use the following text when phoning prospective participants:

Guten Tag, meine Name ist XXX von Audika. Wir führen eine klinische Studie über Hörgeräte durch und wollten Sie anfragen, ob Sie an der Studie teilnehmen möchten.

Die Teilnahme an der Studie umfasst das Tragen von Hörgeräten, Sprachtests und das Beantworten eines Fragebogens über den Anpassungsprozess von Hörgeräten.

Für die Studie werden insgesamt 3 Termine in einer Audika Filiale in Bern oder in Thun erforderlich sein. Zwischen den Besuchen liegt eine Testphase von ca. 10 Tagen, somit wird die

Gesamtstudienzeit ungefähr 1 Monat betragen. Im ersten Termin stellen wir fest, ob Sie für die Studie geeignet sind oder nicht und erklären Ihnen ausführlich den weiteren Ablauf.

Am Ende des Versuchzeitsraumes haben Sie die Möglichkeit die Hörgeräte zu erwerben. Als Dank für Ihre Teilnahme erhalten Sie 100 CHF.

Wenn Sie teilnehmen möchten oder mehr Informationen benötigen, können wir einen Termin vereinbaren.

((When they don't want to make an appointment say:))

Gerne senden wir Ihnen alle Details der Studie noch einmal per Post zu und melden uns bei Ihnen in einer Woche noch einmal. An welche Adresse dürfen wir Ihnen die Unterlagen senden?

((When they choose not to participate say:))

Ich danke Ihnen für ihre Zeit und wünsche Ihnen einen guten Tag.

Do not send the person any information about the trial or contact them again about the trial.

At the appointment, the trial will be explained and Patient Information given to them to read if they have not already received it by mail. They will have time to ask questions.

If it is determined that their hearing loss is appropriate they will be given the opportunity to participate in the trial. If they choose to join the trial, they will be given the consent form to sign. No trial proceedings will begin until the consent form has been signed by the participant and the investigator. The visit described as the screening/V1 will then proceed as per the trial schedule.

### 7.3 Assignment to study group s

The participants are randomized by a block assignment as they appear at the trial sites. There will be 24-40 subjects. The test condition order will be randomized using a 2-factor randomization with a 6 block design. The first factor is the investigator with 4 levels, and the second factor is the test order with 2 levels. This will minimize the bias created when one test condition is tested in the first or last position all of the time.

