### 6.2 Methods of minimi sing bias

#### 6.2.1 Randomisatio n

For the cross-over design, the participants will be divided into two groups. One group will begin the trial with hearing aids programmed with the IMD and the other group will begin the trial with hearing aids programmed with the RMD. Each field trial will last for 10 days (+/-5d). Then they will return to the clinic for an appointment. The allocation to the groups will be randomized using a block randomization method in groups of four. They will be assigned as they appear in the clinics for their appointments. All investigators at the sites should be assigned an equivalent number of participants.

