### 11.2 Determination of Sample Size

A literature search about this tested topic does not provide enough strong references to build a confirmatory analysis. It seems that results might be strongly influenced by the inclusion criteria (first time vs experienced hearing aid users) or test design (cross-over, multi-investigator, or between group designs). There is no article to our knowledge that includes a multi-investigator effect in the test design when looking at the effect of different fitting procedures. Adding a -by investigator- treatment interaction term seems to be mandatory if this trial wants to be determine the effect that different investigators have on the fitting procedure.

The sample size cannot be computed on reported effect sizes from previous experiment; however, the following summary shall be used as an indication to determine the sample size for participants per investigator:

•Naylor et al. (2015) about the narrative effect during the fitting with 24 experienced users and 16 first time users,

•Humes et al. (2017) about the performance with over-the-counter hearing aids compared to audiology best practice with 154 participants,

•Dawes et al. (2013) about the placebo effect in hearing aid trials with 16 experienced hearing aid users,

•Dawes et al. (2011) about the placebo effect in hearing aid trials with 20 experienced hearing aid users.

A placebo effect was found with sample sizes of about 20 participants in a single site study design. Adding an investigator effect in the design might bring new insights in this domain but requires a minimum number of participants per investigator to reduce imbalance between them.

With an effect size of 0.65 from the literature review, 2 degrees of freedom, 24 participants, and an alpha of 0.05, we can achieve a power of 0.82. Therefore, a minimum of 24 participants will be included in the trial overall. There will be 4 investigators with 6 to 8 participants per investigator.

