4.2 Analysis tools	
5. References	8

This test will compared two fitting procedures and devices with the following label:

- Reference Medical Device (RMD): marketed Bernafon device fitted with standardized clinical procedure,
- Investigational Medical Device (IMD): new fitting procedure and device.

While both devices will have the same electro-acoustical performances, it is suspected that changing fitting procedure might influence the subjective benefit for hearing aid user. Research suggest that placebo effect might impact hearing aid trials (Dawes et al., 2013) and that clinician behavior might also modify the perceived benefit of hearing aids (Naylor et al., 2015). The designed test will investigate the potential effect of the IMD compared to the RMD on first time users.

1. Test Design

As the fitting procedure is part of the investigation, no true blinding can be hold. However, the participants will not be told that there is no electro-acoustical difference between IMD and RMD. A balanced cross-over design will be used to guarantee control for period or learning effect. Repeated measures will be analyzed as it reduces the sample size needed to achieve the same test power. No wash out period is needed as it could not be demonstrated that amplification from hearing aid induces a carry-over effect.

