2.1 Primary outcomes

The perceived benefit will be measured with:

- a. the IOI-HA questionnaire and its official translation into German (Cox et al., 2002)
- b. a custom questionnaire based on reference article from Naylor et al. (2015).

These two questionnaires were used in the reference article from Naylor et al. (2015) to measure the effect of narrative embodied in the hearing aid fitting process. Even current research question addresses another aspect of the fitting process, these tools have shown a potential to detect changes in the investigated processes.

IOI-HA questionnaire

Perceived benefit of amplification assessed with 7 questions on a 5 points scale (maximum score 35). Indication from reference study found an effect of fitting process between the preferred and less preferred possibility:

- significant 3.2 scale points and an effect size of 0.68 with experience hearing aid users (n = 24),
- non-significant 0.5 scale points with first time hearing aid users (n = 16).

Custom questionnaire

From the reference study, the questionnaire will directly ask about the preference (much better/slightly better/no difference), the certainty of preference (10 points VAS), and the reason (multiple choice: sound quality, speech intelligibility, listening effort, comfort, loudness, other).

- Fitting procedures: no significant difference between both fitting procedures for first time and experienced hearing aid users,
- Placebo effect: 20 out of 24 indicated a difference with a mean certainty of 7.9/10 for the experienced users group. 14 out of 16 indicated a difference with a mean certainty of 7.0/10 for the first time users group

Order effect

From the reference study, test order might play a different role for first time or experienced users:

- No order effect was found with the experienced hearing aid users,
- A highly significant test order effect in favor for the second tested hearing aid was found for the first time users.

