3.1 Sample size proposal

Sample size cannot be computed on reported effect sizes from previous experiment, however, the following summary shall be used as an indication to determine the sample size for participants per investigator:

- Naylor et al. (2015) about the narrative effect during the fitting with 24 experienced users and 16 first time users. 83% of the experienced HA users had a preference for a given fitting method and 87.5 % for the first time users. Test design was repeated measures and separate analysis on groups based on experience.
- Dawes et al. (2011) about the placebo effect in hearing aid trials with 20 experienced hearing aid users.
 75% of the listeners had a preference for the labelled "new" hearing aid (effect size = 0.50),
- Dawes et al. (2013) about the placebo effect in hearing aid trials with 16 experienced hearing aid users. 75% of the listeners had a preference for the labelled "new" hearing aid (effect size = 0.66),
- Humes et al. (2017) about the performances with over the counter hearing aids compared to audiology best practice with 154 participants. Between groups test design with 3 arms (placebo, reference device, and over the counter alternative).

Placebo effect was found with sample sizes about 20 participants in single site study design. Adding an investigator effect in the design might bring new insights in this domain but need to have a minimum participant per investigator to reduce imbalance between them. A minimum of 24 participants will be included in the test with 4investigators and at least 6 participants per investigator.

This number is in line with Naylor et al. (2015) proposal who wanted "to compare the effect sizes generated by the experimental contrast in this study with those generated in typical studies of alternative HA systems, so we chose a sample size (n = 24) commensurate with such studies. Approximately 75% of studies comparing alternative HA systems utilize $n \le 25$ (Naylor 2005). Statistical power calculations based on HHIE data from another study of a non-acoustical intervention (Thorén et al. 2014) indicate that n = 18 would be sufficient to detect a 10-point change in HHIE score in either direction with an alpha of 0.05 and a Power of 0.8."

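### The blocking scheme is described in two unreconciled ways, so balance of fitting order is not assured under every reading, and the IOI-HA model names no period term to protect the comparison

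*Protocol*

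**What the plan says.** Protocol 6.2.1 states: "The allocation to the groups will be randomized using a block randomization method in groups of four". It names no stratum and asks for equivalent numbers per investigator.

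Protocol 7.3 calls the scheme a "2-factor randomization with a 6 block design" and adds: "The first factor is the investigator with 4 levels, and the second factor is the test order with 2 levels".

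On numbers, Protocol 11.2 says: "There will be 4 investigators with 6 to 8 participants per investigator". SAP 3.1 says: "A minimum of 24 participants will be included in the test with 4investigators and at least 6 participants per investigator". Protocol 7.3 allows 24 to 40 participants in total.

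On the purpose of balance, SAP section 1 (Test Design) says: "A balanced cross-over design will be used to guarantee control for period or learning effect". SAP 2.1 reports from its reference study: "A highly significant test order effect in favor for the second tested hearing aid was found for the first time users". Protocol 7.1 admits first-time users only.

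On the model, SAP 4.1 and Protocol 11.4 specify a linear mixed-effect regression for the IOI-HA. SAP 1.3 adds investigator as a random effect and an investigator-by-treatment interaction. Neither document names a period or sequence term.

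**The concern.** Two people could build different randomisation lists from 6.2.1 and 7.3, and the lists would balance order to different degrees. That would matter little if the analysis adjusted for period. As written, balance is the only stated protection against an effect that the SAP itself reports for this type of participant.

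If the two sequences are unequal and period is not modelled, part of the difference between first and second period is counted as a difference between the IMD and the RMD. Unequal sequences within an investigator do the same to that investigator's contrast, and so to the planned investigator-by-treatment interaction.

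The balance achieved at randomisation can also be lost later. Protocol 11.5 restricts analysis to complete cases and removes data whose accuracy is doubted, and Protocol 8.4 drops data when wear time is too low.

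**Working it through.** **The plan's own figure.** The minimum of 24 rests on a power of 0.82 for the three-outcome preference test (Protocol 11.2, SAP 3.2). With non-centrality 24 × 0.65² = 10.14, 2 degrees of freedom and α = 0.05, I get 0.821, so the figure reproduces. It does not depend on how order is blocked. The plan gives no figure for balance, so the rest is new.

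**Inputs.** Four investigators with six to eight participants each (Protocol 11.2), blocks of four (6.2.1), and two orders allocated 1:1 (Protocol synopsis).

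**Reading 1: one central list in blocks of four.** 24/4 = 6 complete blocks, so 12:12 overall is certain among those randomised. Within an investigator, order is left to chance. If investigators are assigned at random, six each:
- P(3:3 for one investigator) = C(12,3)²/C(24,6) = 48,400/134,596 = 36.0%.
- P(3:3 for all four) = [12!/(3!)⁴]² / [24!/(6!)⁴] = 5.9%.

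**Reading 2: blocks of four within investigator, six each.** The second block stops after two participants. The chances are AA 1/6, BB 1/6 and mixed 4/6, so an investigator is 3:3 with probability 2/3 and 4:2 or 2:4 with probability 1/3.
- P(all four investigators 3:3) = (2/3)⁴ = 19.8%.
- The overall split comes from the coefficients of (1 + 4x + x²)⁴, which sum to 6⁴ = 1,296:

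| Split | Ways out of 1,296 | Probability |
|---|---|---|
| 12:12 | 454 | 35.0% |
| 13:11 | 608 | 46.9% |
| 14:10 | 200 | 15.4% |
| 15:9 | 32 | 2.5% |
| 16:8 | 2 | 0.2% |

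At eight each, two complete blocks of four give 4:4 with certainty.

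**Reading 3: blocks of six within investigator.** At six each, 3:3 and 12:12 are certain. At eight each, an incomplete block remains and each investigator has a 40% chance of 5:3.

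**Effect on the contrast.** Let π be the second-minus-first period effect. Participants who have the IMD first show IMD − RMD = τ − π, and those who have the RMD first show τ + π. With no period term, the estimate averages these to τ + π(n_RMD-first − n_IMD-first)/N. The share of π absorbed at N = 24 is:
- 13:11: 2/24 = 8.3%.
- 14:10: 4/24 = 16.7%.
- Within one investigator at 4:2: 2/6 = 33%.

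The documents give neither the size nor the scale of the order effect. Assuming π of 1 to 3 IOI-HA points:
- 13:11: 0.083 × 1 to 0.083 × 3 = 0.08 to 0.25 points.
- 14:10: 0.167 × 1 to 0.167 × 3 = 0.17 to 0.50 points.

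**Cost of a period term.** The adjusted estimate averages the two sequence means with equal weight. Its variance relative to a balanced trial is N²/(4·n₁·n₂):
- 13:11: 576/572 = 1.007.
- 14:10: 576/560 = 1.029.

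**The case against.** The two sections need not conflict. Six blocks of four make exactly 24, the minimum sample, so the six in 7.3 can be a number of blocks. The overall split is then 12:12, and the SAP promises a balanced design without saying that balance must hold within investigator. A stricter version would even give 3:3 throughout. There are exactly six arrangements of two A and two B in a block of four. If each is used once, with one participant per investigator in each block, every investigator has three of each order. This answers anyone who infers that the sections contradict each other outright, or that only blocks of six could balance order within investigator. Neither inference stands. But the documents do not state this scheme, so what remains is ambiguity.

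It is also fair that imbalance under the adverse reading is usually small: 97% of splits are 14:10 or closer. Its direction is random, so it averages to zero over repeated randomisations. A reader might extend the range to a bias of 1.0 point and set it against the 0.5 points that SAP 2.1 cites for first-time users. The documents do not support that. It needs a 16:8 split (0.2%) together with the largest assumed order effect, and the 0.5 points is a difference between the preferred and less preferred option, not between two fitting methods.

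Finally, SAP 4.1 is a short list of methods that sets out no fixed effects in full. The missing period term may be under-specification and not a decision to leave it out. That is a reason to write it down.

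**Conclusion.** The point holds as an ambiguity in the randomisation with an avoidable gap in the model. It does not show that the trial will be unbalanced. Overall balance is assured under a central list in blocks of four, and balance at both levels under blocks of four within investigator at eight each or blocks of six at six each. It is not assured under blocks of four within investigator at six each, where 12:12 has a 35% chance. No scheme protects it against later exclusions.

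The likely distortion of the IOI-HA contrast is modest: 8% of the order effect at the most probable split and 17% at 14:10. In points it rests wholly on the assumed order effect of 1 to 3. It should still be corrected, because the SAP itself reports a strong order effect in first-time users and the remedy is nearly free. The power figure of 0.82 is unaffected.

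**What to change.** In SAP 4.1 and Protocol 11.4, specify period as a fixed effect in the IOI-HA mixed model, beside fitting method, investigator and investigator-by-treatment. This removes the order effect from the IMD-RMD contrast under every reading of the blocking and after imbalance caused by exclusions. It costs one degree of freedom and about 0.7% (13:11) to 2.9% (14:10) more variance.

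Also reconcile Protocol 6.2.1 and 7.3 into one scheme that says whether order is stratified by investigator. Keep the block size in a separate randomisation document that is not held at the sites: the trial is open label, and Protocol 12.1.2 places the protocol in each site file. Block size alone cannot carry the balance. Four fails at six per investigator, six fails at eight, and no fixed size balances seven. The cost is a short text change before the list is generated.

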### 7.4 Criter ia for withdra wal / discontinuation of participants

Participants are allowed to withdraw from the study at any time and for any reason. They do not have to share the reasons with the investigator. They will be asked to return the hearing aids. If the decision is made by the investigator then they will inform the participant in person that they are no longer needed for the study. Reasons for withdrawing a participant from the study could be for non-compliance during testing, unreliable responses, medical reasons such as an ear infection, or the study may need to be stopped or postponed. Any data gathered from these subjects will be used for the current study. All data will remain encoded because results are only recorded using the identification code of the subject. There will be at least 5 "back-up" test participants to replace those that withdraw or are withdrawn. These are participants that have already been screened and determined to be appropriate for the testing.

# 8. STUDY INTERVENTION

### 8.1 Identity of Investigationa | Products (medical device)

The treatment will be approximately 1 month of use overall with hearing aids. During half of this time the participants will use hearing aids programmed with the IMD and during the other half the hearing aids will be programmed with the RMD.

There are 2 field test periods planned. They will continue wearing the hearing aids throughout both field tests and only have them reprogrammed at Visit 2. There is no need for a washout period or breaks between the fittings because amplification from hearing aids do not induce a carry-over effect.

At the end of the trial, the participants will return all hearing aids. They will have the option to purchase hearing aids, but they will be new serial numbers and not the devices used during the trial.

[figure not shown]
#### 8.1.1 Experimental Intervention (treatment / medical device)

The investigational product (IMD) is a medical device. It is a new self-directed software that combines a hearing screening and the hearing aid fitting into one procedure. The name of the software is HearToo Studio. The hearing aid that the software will program for the trial is already CE marked and sold on the market for 2 years. It still has the same intended use and the basic function of amplifying sound.

The IMD will produce automated tones at a frequency range of 250 Hz to 8000 Hz with an output limit of 80 dB. A standard audiometer has an output of up to 120 dB at certain frequencies. The IMD only has an output of 80 dB to mitigate the risk of a person allowing the system to present too loud of tones by not responding. The user will respond when they hear the tone. The IMD transfers the screening results to a restricted version of Oasis software to implement the results into the hearing aid fitting. Traditionally, these results are input manually by the HCP into the software. The software will use the screening results to quantify the amount of amplification needed in the hearing aid in the same manner that it does in the current Oasis software. Performance is expected to be the same when programmed with the IMD as it is with the RMD because both fitting methods will use the IMD screening results to calculate gain. The hearing aids when programmed with either method will be the same electro-acoustically.

The version of Oasis software is a restricted and simplified version. There will only be 3 styles of hearing aids offered and one type of acoustics. Therefore, decisions that HCPs would normally have to make with the standard software have been removed and are automatically chosen in the software. The HCP cannot fit multiple programs to the hearing aid with the IMD, only one. They also can make simple fine-tuning as seen in the picture below. In the standard version of the software the HCP can adjust specific frequencies and input levels, as well as adjust features.

The new software is a non-invasive device. It uses supra-aural headphones to conduct the hearing screening. The hearing aid itself is worn behind/over the ear with a part that fits into the ear canal. The part that fits in the ear canal is either made of silicon or plastic that is covered with an acrylic coating (for custom molds or ITEs). The hardware of the BTE is painted with a non-toxic paint. Below is a picture of the process of the IMD. First the hearing screening, then the hearing fitting, and finally the settings are saved to the hearing aids.

Sound Overall Volume	Speech Own Voice Other Voices
Loud Sounds Soft Sounds	Balance Sound Fuller Fuller
Reduce	Feedback Both Keft

Amplification

